7.5 SECONDARY ENDPOINTS

7.5.1 Key secondary endpoint

Not applicable.

7.5.2 Secondary endpoints

The analysis of secondary endpoints will be based on the PKS.

The secondary endpoints will be assessed statistically using the same methods as described for the primary analysis of the primary endpoints.

7.7 EXTENT OF EXPOSURE

Descriptive statistics are planned for this section of the report.

7.8 SAFETY ANALYSIS

All safety analyses will be performed on the TS.

7.8.1 Adverses Events

AEs will be coded with the most recent version of MedDRA. The Residual Effect Period (REP) of alteplase is 24 hours (i.e. 23.5h after end of infusion) in this trial, see CTP Section 1.2.3.

The analyses of AEs will be descriptive in nature. All analyses of AEs will be based on the number of subjects with AEs and not on the number of AEs.

For further details on summarization of AE data, please refer to "Analysis and Presentation of Adverse Event Data from Clinical Trials" (7) and "Handling of missing and incomplete AE dates" (3).

The analysis of AEs will be based on the concept of treatment emergent AEs. That means that all AEs will be assigned to screening or on-treatment phases as defined in [Section 6.1](#). AEs will be analysed based on actual treatments, as defined in [Table 6.1: 1](#).

An overall summary of AEs will be presented. This overall summary will comprise summary statistics for the class of other significant AEs according to ICH E3 (8) and for the class of AESIs.

CTP Section 5.2.6.1.4: *The following are considered as AESIs:*

- *Hepatic injury*
A hepatic injury is defined by the following alterations of hepatic laboratory parameters:
 - *An elevation of AST (aspartate transaminase) and/or ALT (alanine transaminase) ≥ 3 -fold ULN combined with an elevation of total bilirubin ≥ 2 -fold ULN measured in the same blood sample, or*

- *Aminotransferase (ALT, and/or AST) elevations ≥ 10 fold ULN*

The investigator had to classify on the eCRF whether an observed AE was an AESI or not.

According to ICH E3 (8) AEs classified as "other significant" need to be reported and will include those non-serious and non-significant AEs

- (i) which are marked haematological or other lab abnormalities, or
- (ii) which were reported with "action taken = discontinuation" or "action taken = reduced", or
- (iii) which lead to significant concomitant therapy as identified by the Clinical Monitor/Investigator at a Medical Quality Review Meeting.

The frequency of subjects with AEs will be summarised by treatment, primary SOC and preferred term. AEs which were considered by the investigator to be drug related will be summarised separately. Separate tables will also be provided for subjects with SAEs, subjects with AESIs and subjects with other significant AEs (according to ICH E3 (8)). AEs will also be summarized by maximum intensity.

The SOCs and preferred terms within SOCs will be sorted by descending frequency over all treatment groups.

For disclosure of AE data typically intended for ClinicalTrials.gov, the frequency of subjects with non-serious AEs occurring with an incidence of greater than 5 % (in preferred terms) will be summarised by treatment, primary SOC and preferred term. The frequency of subjects with SAEs will also be summarised.

For disclosure of AE data in the EudraCT register, the frequency of AEs, the frequency of non-serious AEs with an incidence of greater than 5 % (in preferred terms) and the frequency of SAEs will be summarized.

For support of lay summaries, the frequency of subjects with drug-related SAEs will be summarized by treatment, primary SOC and preferred term.

7.8.2 **Laboratory data**

The analyses of laboratory data will be descriptive in nature and will be based on BI standards "Display and Analysis of Laboratory Data" (9).

Analyses will be based on normalised values, which mean transforming to a standard unit and a standard reference range. The original values will be analysed if the transformation into standard unit is not possible for a parameter.

Descriptive statistics of absolute values and change from baseline from laboratory parameters over time (see [Section 6.7](#)) will be provided. Frequency tables of changes between baseline and last value on treatment with respect to the reference range will be presented.

Individual line plots as well as plots on aggregated data presenting median with Q1 and Q3 as error bars will be provided for plasminogen and α 2-antiplasmin.

Unscheduled measurements of laboratory data will be assumed to be repeat measurements of the most recent scheduled measurement (e.g. for follow-up or confirmation of a particular value). Therefore, unscheduled measurements will be assigned to the planned time point of the previous scheduled measurement. Descriptive statistics will be calculated by planned time point based on the worst value of the subject at that planned time point (or assigned to that planned time point).

Possibly clinically significant abnormal laboratory values are only those identified either in the Investigator's comments or at the RPM at the latest. It is the Investigator's responsibility to decide whether a lab value is clinically significant abnormal or not. Standard or project-specific rules for flagging clinically significant values in an automated manner will not be applied in this study.

Clinically relevant findings in laboratory data will be reported as baseline conditions (prior to first administration of study treatment) or as AEs (after first administration of study treatment) if judged clinically relevant by the investigator, and will be analyzed as such.

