			0:05	08:05				x			
			0:10	08:10				x			
			0:15	08:15				x			
			0:20	08:20				x			
			0:25	08:25				x	x ⁸		
			0:30	08:30	End of infusion		▼	x			x
			0:32	08:32				x			
			0:34	08:34				x			
			0:36	08:36				x			
			0:40	08:40				x			
			0:45	08:45				x			
			0:50	08:50				x			
			1:00	09:00	240 mL fluid intake			x	x ^{8,9}		x
			1:20	09:20				x			
			1:40	09:40				x			
			2:00	10:00	Snack , 240 mL fluid intake			x	x ⁸		x
			3:00	11:00	Assessment of local tolerability			x			x
			4:00	12:00	lunch ³	B		x		x	x
			6:00	14:00				x			x
			7:30	15:30	Snack						
			10:45	18:45	Assessment of local tolerability ¹⁰ (all subjects together)	x ⁷					x ¹⁰
			11:00	19:00	Dinner						
	3	1	-1:30	06:30				x ²	x ^{2,8}	x ²	x ²
			-0:15	07:45		B		x	x ^{8,9}		
			-0:05	07:55	i.v.-bolus of standard heparin						
			0:00	08:00	Start of alteplase infusion		▲				
			0:05	08:05				x			
			0:10	08:10				x			
			0:15	08:15				x			
			0:20	08:20				x			
			0:25	08:25				x	x ⁸		
			0:30	08:30	End of infusion		▼	x			x
			0:32	08:32				x			
			0:34	08:34				x			
			0:36	08:36				x			
			0:40	08:40				x			
			0:45	08:45				x			
			0:50	08:50				x			

Treatments periods will be performed on 2 consecutive days

Proprietary confidential information © 2021 Boehringer Ingelheim International GmbH or one or more of its affiliated companies

			1:00	09:00	240 mL fluid intake			x	x ^{8,9}		x
			1:20	09:20				x			

Period	Visit	Day	Planned time (relative to start of infusion [h:min])	Approximate clock time of actual day [h:min]	Event and comment	Safety laboratory	Alteplase Infusion	PK _{blood} (x) / ADA (y)	Biomarkers ⁸	Vital signs (BP, PR)	Questioning for AEs and concomitant therapy ⁶
3	1	1	1:40	09:40				x			
			2:00	10:00	Snack, 240 mL fluid intake			x	x ⁸		x
			3:00	11:00	Assessment of local tolerability			x			x
			4:00	12:00	lunch ³	B		x		x	x
			6:00	14:00				x			x
			7:30	15:30	Snack						
			10:45	18:45	Assessment of local tolerability ¹⁰ (all subjects at that time)						x ¹⁰
			11:00	19:00	Dinner						
		2	24:00	08:00	Assessment of local tolerability, Breakfast (voluntary), discharge from trial site	B		x ⁸	x	x	
EOT	4		8-22		End of trial (EOT) examination ⁴	C			x	x	

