The studies 135.57 and 135.67 are two bioequivalence trials that were performed 1989 and 1992 in the [REDACTED] in [REDACTED] comparing alteplase derived from two different manufacturing processes. In both trials two groups of 12 subjects (parallel-group design) received an i.v. infusion of 0.25 mg/kg alteplase over 30 min.

In the 135.57 trial mean maximum alteplase concentrations of 774 ng/ml and 739 ng/ml have been achieved. At 1 hour after infusion plasminogen and fibrinogen decreased by about 10% compared to baseline. After 24 hours there was no change of plasminogen and fibrinogen compared to baseline. No adverse events were reported during this trial [[U91-0823](#)].

In the 135.67 trial mean maximum alteplase concentrations of 917 ng/ml and 933 ng/ml have been achieved. One hour after start of infusion plasminogen decreased by 8% and 9% in both treatment groups. The respective decrease of α 2-antiplasmin was -16% and -14%. These changes were not detectable any more at 24 hours. For fibrinogen no directional change was seen. One subject complained about mild nausea at about 2 hours after start of infusion (AE recovered within 1 hour). Otherwise both treatments were well tolerated [[U94-2138](#)].

De Boer et al (1993) reported a trial that investigated the effect of nifedipine (20 mg p.o.) on endogenous and recombinant tissue-type plasminogen activator (t-PA and rt-PA). Following a randomized, three-way cross-over design with a wash-out period of one week between the treatments nine healthy subjects received an intravenous infusion of 35 mg rt-PA over 120 min with nifedipine capsules (a), with placebo nifedipine capsules (b) and an i.v. saline infusion over 120 min with nifedipine (c). According to Figure 2 in this paper maximum plasma concentrations of total rt-PA antigen at the end of infusion were in the range of 700 – 800 ng/ml. With the exception of vasovagal reactions in one subject the authors did not report adverse events from this trial. All subjects completed the study [[P93-77079](#)].

Proprietary confidential information © 2021 Boehringer Ingelheim International GmbH or one or more of its affiliated companies

[figure not shown]
Proprietary confidential information © 2021 Boehringer Ingelheim International GmbH or one or more of its affiliated companies

Proprietary confidential information © 2021 Boehringer Ingelheim International GmbH or one or more of its affiliated companies

[figure not shown]

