1.5.2 Risk resulting from the trial design

In this cross-over trial two single doses of alteplase (0.2 mg/kg) will be infused on 2 consecutive days keeping a wash-out period of at least 24 hours. This short interval has been chosen to prevent any effect of potentially formed anti-drug antibodies on alteplase kinetics.

Considering the short beta-half-life of alteplase of about 40 min this wash-out period is justified. In the sister trials 135.57 and 135.67 laboratory parameters of fibrinolytic system (fibrinogen, plasminogen and α_2 -antiplasmin) were only minimally affected by a chosen dose of 0.25 mg/kg alteplase (infusion in 30 min) and after 24 hours these changes were not detectable any more [[U91-0823](#), [U94-2138](#)]. Considering that there is neither a PK- nor a PD-overlap no undue risk to healthy subjects is expected from the chosen wash-out period.

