6.2.3 Follow-up period and trial completion

The EOT visit will be performed at least 1 week after the last trial drug administration within the time span defined in the [Flow Chart](#).

For AE assessment, laboratory tests, recording of ECG and vital signs, and physical examination during the follow-up period, see Sections [5.2.2](#) to [5.2.5](#).

Subjects who discontinue treatment before the end of the planned treatment period should undergo the EoTrial Visit.

All abnormal values (including laboratory parameters) that are assessed as clinically relevant by the investigator will be monitored using the appropriate tests until a return to a medically acceptable level is achieved. (S)AEs persisting after a subject's EoTrial Visit must be followed until they have resolved, have been sufficiently characterised, or no further information can be obtained.

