6. GENERAL ANALYSIS DEFINITIONS

6.1 TREATMENTS

For basic study information on treatments to be administered, assignment of treatment groups, and selection of doses, cf. Section 4 of the CTP.

All subjects will receive the 2 treatments (TPA-02 and TPA-05) in randomised order at 2 consecutive days. The specific alteplase dose to be administered to a given subject will be calculated based on the body weight measured at screening examination. Prior to the first administration of trial medication, subjects will be assigned to treatment sequences T-R or R-T.

For statistical analysis of AEs, safety laboratory data, vital signs and ECG, the following analysis phases are defined for each subject:

Table 6.1: 1 Flow chart of analysis phases for statistical analyses of AEs, safety laboratory and vital signs

Study analysis phase	Label	Start (inclusive)	End (exclusive)
Screening	Screening	Date of informed consent	Date/time of first administration of TPA-02/ TPA-05
On-treatment	TPA-02 0.2 mg/kg body weight	Date/time of first administration of TPA-02	Date/time of first administration of TPA-05 or 12:00 a.m. on day after subject's trial termination date, whichever occurs earlier
On-treatment	TPA-05 0.2 mg/kg body weight	Date/time of first administration of TPA-05	Date/time of first administration of TPA-02 or 12:00 a.m. on day after subject's trial termination date, whichever occurs earlier

Analysis phases for statistical analysis of AEs are defined for each subject as described in the table above.

CTR Section 15, Appendix 16.1.13.1.8.2 and Appendix 16.1.13.1.8.3 AE displays will present results for the on-treatment phase and screening phase.

In CTR Section 15 AE tables (but not in Appendix 16.1.13.1.8.2 and Appendix 16.1.13.1.8.3 AE tables), the following totals will be provided in addition:

- **"Total on-trt"**, defined as the total over all on-treatment phases involving BI

Safety laboratory data and vital signs will be analysed by treatment (TPA-02 or TPA-05).

More details on the technical implementation of these analyses are provided in the ADS Plan of this TSAP.

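### The SAP 7.8.2 laboratory shift tables leave out the 4 h panel and mix roughly 24 h values with values at least a week post-dose within each product

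*SAP*

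**What the plan says.** On laboratory data, SAP 7.8.2 plans descriptive statistics over time and one reference-range display: "Frequency tables of changes between baseline and last value on treatment with respect to the reference range will be presented". Where a time point has repeat measurements, the descriptive statistics are "based on the worst value of the subject at that planned time point".

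What counts as on treatment is set by SAP Table 6.1: 1, titled "Flow chart of analysis phases for statistical analyses of AEs, safety laboratory and vital signs". The TPA-02 phase ends at "Date/time of first administration of TPA-05 or 12:00 a.m. on day after" the subject's trial termination, whichever comes first, and the TPA-05 row mirrors it. There is no follow-up phase. Protocol 7.3.4, in contrast, ends the treatment period at the 24 h residual effect period and assigns later events to follow-up.

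The protocol Flow Chart places panel B at -0:15 and 4:00 in both periods. A further panel B falls at 24:00 after the second infusion, in the row "Assessment of local tolerability, Breakfast (voluntary), discharge from trial site". Panel C is taken at the end-of-trial visit, and Protocol 6.2.3 adds: "The EOT visit will be performed at least 1 week after the last trial drug administration". Protocol Table 5.2.3: 1 includes aPTT, INR and fibrinogen in both B and C.

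**The concern.** The drugs act over minutes to hours. Protocol 1.5.2 says of fibrinogen, plasminogen and alpha2-antiplasmin in the two earlier alteplase trials that "after 24 hours these changes were not detectable any more". For one of those trials, Protocol 1.2.4 reports: "After 24 hours there was no change of plasminogen and fibrinogen compared to baseline". A table that compares baseline with a sample at about 24 h or later describes recovery. It does not show whether subjects left the reference range while the drugs were acting.

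This matters here because Part A was stopped for procoagulant effects (Protocol 3.1) and Part B adds a heparin bolus before each alteplase infusion. The shift table is the only reference-range tabulation of subjects that the SAP text names. As defined, it gives no information about the 4 h panel, and its entries for one product do not share a common time since dosing.

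**Working it through.** There is no planned figure to reproduce. The check is to place each scheduled panel in its phase, take the last one, and see what would remain of each drug at that time.

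**Step 1: last value in each phase.** Infusion starts are at least 24 h apart (Protocol 6.2.2). At the minimum spacing, the Visit 3 pre-dose panel falls at 24:00 − 0:15 = 23:45 after the first infusion started. It precedes the second product's first dose, so Table 6.1: 1 puts it in the first product's phase. The same sample is also the period 2 baseline (SAP 6.7).

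| Product given | Scheduled panels after infusion start | Last value under Table 6.1: 1 |
|---|---|---|
| First | B at 4:00; B at 23:45 | 23:45 |
| Second | B at 4:00; B at 24:00; C at end of trial (7 × 24 = 168 h or later) | End of trial; 24:00 if that is missing |

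The 4:00 panel is last only if every later panel in that phase is missing.

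**Step 2: mixture within a product.** Sequences are allocated 1:1 (Protocol 7.6). With 18 evaluable and balanced stage 1 subjects, each product's table would hold about 9 values at 23:45 and about 9 at 168 h or later. At the Part B maximum of 18 + 42 = 60 the split is about 30 and 30.

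**Step 3: what remains at each time.** Fraction remaining = 2^(−t / half-life). Half-lives are about 40 min for the alteplase beta phase (Protocol 1.2.1) and 90–120 min for heparin (Protocol 1.3). Alteplase is timed from the end of the 30 min infusion, and heparin from the bolus 5 min before the infusion starts.

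- Alteplase at 4:00: (240 − 30) / 40 = 5.25 half-lives, about 2.6% remaining.
- Alteplase at 23:45: (1425 − 30) / 40 = 34.9 half-lives, about 3 × 10⁻¹¹ remaining.
- Heparin at 4:00: 245 / 120 to 245 / 90 = 2.0 to 2.7 half-lives, 24% to 15% remaining.
- Heparin at 23:45: 1430 / 120 to 1430 / 90 = 11.9 to 15.9 half-lives, less than 0.03% remaining.

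The 4:00 panel is therefore the only scheduled aPTT, INR and fibrinogen measurement at which a meaningful part of the heparin bolus could still be present.

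**The case against.** The strongest reply is that the 4 h data are reported elsewhere. SAP 7.8.2 gives by-time-point statistics, and SAP 7 specifies that these include minimum and maximum. Protocol 7.3.4 highlights out-of-range values in the listings. Findings judged clinically relevant become AEs, which are counted by subject and treatment, with a class that covers marked laboratory abnormalities (SAP 7.8.1). With 18 to 60 subjects, anyone can count from the listings. A reader might infer that the 4 h values are discarded, or that a relevant abnormality with one product would go unseen. The documents support neither inference.

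Other points also stand:

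- Acute coagulation is followed through separate biomarkers and a safety review after the first two cohorts (Protocol 3.1).
- The earlier trials used 0.25 mg/kg. One hour readings of fibrinogen showed a fall of about 10% in one trial and no directional change in the other, so they give no reason to expect low fibrinogen at 4 h. They are not cited for aPTT or INR, and for aPTT the argument rests on the heparin half-life.
- Plasminogen and alpha2-antiplasmin are not in panel B.
- A baseline-to-last table is a legitimate display of recovery.
- The sponsor's laboratory display standard (SAP reference 9) and the ADS Plan are not available here and may add tables.

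These points limit the consequence. They do not change how the named table is built, and none of the outputs described in the protocol or SAP is a by-product count of subjects moving out of range at 4 h.

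**Conclusion.** The point holds as a defect in one descriptive safety table. With complete sampling, the shift table omits the 4:00 panel for every subject in both periods and mixes 23:45 h values with values at least 168 h post-dose within each product. Nothing in the bioequivalence analysis depends on it.

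Two assumptions carry this. First, the Visit 3 pre-dose sample counts as on treatment for the first product, as Table 6.1: 1 implies, and not only as the period 2 baseline. Second, the second product's phase runs to trial termination. Read literally, the whichever-is-earlier rule would end that phase at the other product's dose on the previous day, before the phase begins.

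Two further inferences are tempting and should not be drawn:

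- A reader might infer that the problem would survive a cut of the phase at the 24 h residual effect period. That holds for period 1 (23:45). In period 2 it depends on the boundary: if the end is exclusive, as in Table 6.1: 1, the nominal 24:00 sample drops out and the 4:00 value becomes the last.
- A reader might infer that the SAP already has a worst-value rule that covers this. That rule handles repeats assigned to one planned time point and does not look across time points.

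**What to change.** In SAP 7.8.2, replace the baseline-to-last table with one of two forms:

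- shift tables from the period baseline by nominal post-dose time point: 4:00, and about 24 h (Visit 3 pre-dose for period 1, 24:00 for period 2); or
- shift tables from the period baseline to the lowest and to the highest value over those same nominal time points.

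Show end-of-trial values in a separate shift table. Define the window by nominal time points and not by a strict 24 h clock: laboratory samples have a ±30 min tolerance (Protocol 6.1), so a clock cut would include or drop 24:00 samples by minutes. Reconcile the SAP phases with the follow-up phase in Protocol 7.3.4, and correct the rule in Table 6.1: 1 that ends the second product's phase.

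The cost is a short text edit and some reprogramming, with no new data. There are two small downsides. Slightly more isolated out-of-range values will be counted. Shifts in aPTT at 4 h may also largely reflect the heparin bolus given before both products, so the table should carry a note to that effect.

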7.8.3 Vital signs

The analyses of vital signs (blood pressure and pulse rate) will be descriptive in nature. Descriptive statistics of absolute values and change from baseline from vital signs over time (see [Section 6.7](#)) will be provided.

Unscheduled measurements of vital signs will be assigned to planned time points in the same way as described above for laboratory data. However, for vital signs, descriptive statistics will be calculated by planned time point based on the last value of the subject at that planned time point (or assigned to that planned time point).

Clinically relevant findings in vital signs data will be reported as baseline conditions (prior to first administration of study treatment) or as AEs (after first administration of study treatment) if judged clinically relevant by the investigator, and will be analyzed as such.

7.8.4 ECG

Abnormal findings will be reported as baseline conditions (prior to first study drug administration) or as AEs (from first study drug administration onwards) if judged clinically relevant by the investigator.

7.8.5 Others

Physical examination findings will be reported as relevant medical history/baseline condition (if a condition already exists before first administration of study treatment) or as AE (if condition emerges after first administration of study treatment) and will be summarized as such. No separate listing or analysis of physical or neurological examination findings will be prepared.

